3.4.1 Baseline for PDAI, ABSIS, ABQOL, TABQOL and SNAQ scores

The value measured at Week 1 Day 1 pre-dose will be used as the Baseline value. If the Week 1 Day 1 Pre-dose result is missing and the screening result is available, then the screening result will be used as Baseline.

3.4.2 Baseline for Lab and Vital Signs

The value measured at Week 1 Day 1 pre-dose will be used as the Baseline value. If the Week 1 Day 1 pre-dose result is missing and the screening result is available, then the screening result will be used as Baseline.

3.4.3 Pre-treatment vs. treatment emergent vs. post last dose adverse events

Pre-treatment events are the events that started prior to the first study drug dosing.

Treatment emergent adverse events (TEAEs) are the events started on or after the first study drug.

Post last dose adverse events are the events that started after the last date of study drug dosing.

3.4.4 Prior medications vs. concomitant medications vs. post last dose medications

Prior medications are the medications stopped before the date of first study drug dosing.

Concomitant medications are the medications that are ongoing or stopped after the date of first study drug dosing and started on or prior to the last date of study drug dosing.

Post last dose medications are medications that started after the last date of study drug dosing.

3.4.5 Study Day

The date of first study drug dosing is considered as Study Day 1.

- Study Day = (Date of assessment – date of first dose in Part B + 1), if the assessment date is on or after the date of first dose in Part B.
- Study Day = (Date of assessment – date of first dose in Part B), if the assessment date is prior to the date of first dose in Part B.

3.4.6 Time from Pemphigus Diagnosis (years)

Time from event (years) = (Date of screening – First date of Pemphigus reported in Medical History + 1)/365.25

3.4.7 Control of Disease Activity (CDA), Complete Remission (CR), End of Consolidation Phase (ECP) and Relapse

Control of Disease Activity (CDA) is defined as the time at which new lesions cease to form and established lesions begin to heal. This is also considered the beginning of the consolidation phase. Date of CDA should be the first date CDA occurred i.e. a visit date or earlier date reported by the patient. If there is a relapse and a subsequent second CDA, visits from that second CDA visit forward would record the date of the second CDA. If CDA is yes, relapse must be no.

Complete remission (CR) in this study is defined as the complete healing of all lesions and absence of new lesions on any dose of corticosteroid or no steroids. Date of CR should be the first date CR occurred i.e. a visit date or earlier date reported by the patient. The duration of time in CR e.g. 8 weeks is not included in the definition. If CR is yes, CDA, ECP must be yes also, and relapse must be no.

End of Consolidation Phase (ECP) is defined as the time at which no new lesions have developed for a minimum of 2 weeks and the majority (approximately 80%) of established lesions have healed. It is at this point that most clinicians begin to taper corticosteroid doses. Date of ECP should be the first date ECP occurred i.e. a visit date or earlier date reported by the patient. If ECP is yes, CDA must be yes also, and relapse must be no.

Relapse (i.e. flare) is defined by the appearance of 3 or more new lesions in a month that do not heal spontaneously within 1 week, or by the extension of established lesions, in a patient who has achieved control of disease (i.e. CDA). Date of relapse should be the first date relapse occurred i.e. a visit date or earlier date reported by the patient. If relapse is yes, CDA, ECP and CR must be no.

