141 DAYS	xx.x (xx)	xx.x (xx)	xx.x (xx)	xx.x (xx)
169 DAYS	xx.x (xx)	xx.x (xx)	xx.x (xx)	xx.x (xx)

Note: Patients are classified into different dose levels according to the maximum dose they received during the 12 week treatment period. Control of disease activity (CDA) is defined as the time at which new lesions cease to form and established lesions begin to heal.

[1] Time to first CDA = Date of first CDA confirmed - Date of first dose + 1. Patients who did not achieve CDA by the date of study completion or discontinuation were censored at the date of completion or discontinuation respectively. 80% and 95% confidence intervals are calculated using the LOGLOG transformation.

[2] * indicate that this value is from a censored data.

[3] Kaplan-Meier estimate of the probability of experiencing the event on or before the specified timepoint (n' = number of patients remaining at risk beyond the specified timepoint).

Source Data: Listing 16.2.4.1.6

<DIRECTORY PATH>PROGRAM NAME Executed: DDMMYYYY hh:mm

Repeat the table above with the following population.

Table 14.2.3.1.2

Time to First Control of Disease Activity (CDA): Kaplan Meier Estimates
mITT Population

Table 14.2.3.1.3

Time to First Control of Disease Activity (CDA): Kaplan Meier Estimates
Per Protocol Population

Table 14.2.3.2.1
Time to First Complete Response (CR): Kaplan Meier Estimates
ITT Population

	400 mg (N=xx)	500 mg (N=xx)	600 mg (N=xx)	Total (N=xx)
TIME TO FIRST CR (days) [1]				
n	xx	xx	xx	xx
25% QUARTILE	xx.x	xx.x	xx.x	xx.x
80% CONFIDENCE INTERVAL	(xx.x, xx.x)	(xx.x, xx.x)	(xx.x, xx.x)	(xx.x, xx.x)
95% CONFIDENCE INTERVAL	(xx.x, xx.x)	(xx.x, xx.x)	(xx.x, xx.x)	(xx.x, xx.x)
MEDIAN	xx.x	xx.x	xx.x	xx.x
80% CONFIDENCE INTERVAL	(xx.x, xx.x)	(xx.x, xx.x)	(xx.x, xx.x)	(xx.x, xx.x)
95% CONFIDENCE INTERVAL	(xx.x, xx.x)	(xx.x, xx.x)	(xx.x, xx.x)	(xx.x, xx.x)
75% QUARTILE	xx.x	xx.x	xx.x	xx.x
80% CONFIDENCE INTERVAL	(xx.x, xx.x)	(xx.x, xx.x)	(xx.x, xx.x)	(xx.x, xx.x)
95% CONFIDENCE INTERVAL	(xx.x, xx.x)	(xx.x, xx.x)	(xx.x, xx.x)	(xx.x, xx.x)
MIN, MAX [2]	xx, xx	xx, xx*	xx, xx	xx*, xx
KAPLAN-MEIER ESTIMATE % (n') [3]				
15 DAYS	xx.x (xx)	xx.x (xx)	xx.x (xx)	xx.x (xx)
29 DAYS	xx.x (xx)	xx.x (xx)	xx.x (xx)	xx.x (xx)
57 DAYS	xx.x (xx)	xx.x (xx)	xx.x (xx)	xx.x (xx)
85 DAYS	xx.x (xx)	xx.x (xx)	xx.x (xx)	xx.x (xx)
113 DAYS	xx.x (xx)	xx.x (xx)	xx.x (xx)	xx.x (xx)
141 DAYS	xx.x (xx)	xx.x (xx)	xx.x (xx)	xx.x (xx)
169 DAYS	xx.x (xx)	xx.x (xx)	xx.x (xx)	xx.x (xx)

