5.4.1 Primary Efficacy Endpoint

The primary efficacy endpoint is:

- The proportion of patients who are able to achieve CDA within 4 weeks (on or prior to Week 5 visit) of starting PRN1008 treatment **without** the need for doses of prednis(ol)one > 0.5 mg/kg

The Control of Disease Activity (CDA) responses are assessed at visits specified in the Schedule of assessments (Table 1). Types of CS other than prednis(ol)one are converted to dose-equivalent prednis(ol)one (see Section 5.4.2.3).

This is operationalized as meaning the first CDA is achieved on or before the Week 5 visit but after first dose of PRN1008, and will be summarized, by dose level to the Week 5 visit and overall in a table, using frequencies and percentages. In addition, two-sided 80% and 95% CIs (Confidence Intervals) of the response rate will be provided for each dose level and overall.

Patients who are able to achieve CDA between first dose of study drug and the Week 5 visit without prednis(ol)one >0.5 mg/kg on the date prior to the CDA will be considered as responders, even if the CDA status was not maintained or higher doses of prednis(ol)one were used after the first CDA. Patients who are not able to achieve CDA prior to or at the Week 5 visit or had prednis(ol)one >0.5 mg/kg on the date prior to CDA will be considered as non-responders. Patients whose CDA status is unknown at the Week 5 visit for whatever reason (including early termination before Week 5 visit) will be also considered as non-responders. Only systemic CSs (as defined by medication taken orally or intravenously) are to be used to evaluate the efficacy endpoints, topical CSs (including buccal CS) will not be counted.

The number and percentage of patients who meet the primary efficacy endpoint criteria will be tabulated by dose level and overall (all patients).

A sensitivity analysis using the Completer and PP population will be provided.

Panel plots will be provided for PDAI score over the study period for each patient. Dose level (mg/day) will also be plotted on the same figure. Lines for the steroid equivalent dose in mg/kg will be added to the plots. A total of 9 plots (3 x 3) will be fitted on one page.

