Compliance with study drug = the actual number of doses taken divided by the expected number of doses take, expressed as a percentage.

Program: <program name (date, time)>, Path: <path>

Listing B.16.2.6.1 Disease Assessment (ITT Population)

Starting Dose	Patient ID	Age/ Gender	Visit	Current PRN Dose	Control of Disease Activity (CDA) Status Achieved at this visit If Yes, Date (ddMMMyyyy)	Complete Remission (CR) Status Achieved at this visit If Yes, Date (ddMMMyyyy)	End of Consolidated Phase Status Achieved at this visit If Yes, Date (ddMMMyyyy)	Relapse Status Achieved at this visit If Yes, Date (ddMMMyyyy)
400 mg QD	xxxxxxx	xx/F	xxx	400 mg QD	No	No	No	No
			xxx	400 mg QD	Yes – ddMMMyyyy	No	No	No

F=Female; M=Male

Program: <program name (date, time)>, Path: <path>

Listing B.16.2.6.2 Pemphigus Disease Area Index (PDAI) - Skin (ITT Population)

Starting Dose	Patient ID	Age/ Gender	Visit	Current Dose	Date if PDAI (ddMMMMyyyy)	Total Skin (/120) – Activity	Total Skin (/12) – Damage	Anatomical Location	Erosion /blister or new erythema	Number Lesion if <=3	Post-inflammatory hyperpigmentation or erythema from resolving lesions
400 mg QD	xxxxxxx	xx/F	xxx	400 mg QD	xxxx	xx	xx	EARS	xx	xx	Absent
								NOSE	xx	xx	Absent
								REST OF THE FACE	xx	xx	Present
								...etc..			
	...etc..										

F=Female; M=Male

Program: <program name (date, time)>, Path: <path>

Listing B.16.2.6.3 Pemphigus Disease Area Index (PDAI) - Scalp (ITT Population)

Starting Dose	Patient ID	Age/ Gender	Visit	Current PRN Dose	Date if PDAI (ddMMMyyyy)	Total Scalp (/10) – Activity	Total Scalp (/1) – Damage	Anatomical Location	Erosion /blister or new erythema	Number Lesion if <=3	Post-inflammatory hyperpigmentation or erythema from resolving lesions
400 mg QD	xxxxxxx	xx/F	xxx	400 mg QD	xxxx	xx	xx	SCALP	xx	xx	Absent
			xxx	400 mg QD	xxxx	xx	xx	SCALP	xx	xx	Absent
			xxx	400 mg QD	xxxx	xx	xx	SCALP	xx	xx	Present
	...etc..										

F=Female; M=Male

Program: <program name (date, time)>, Path: <path>

Listing B.16.2.6.4 Pemphigus Disease Area Index (PDAI) – Mucous Membrane (ITT Population)

Starting Dose	Patient ID	Age/ Gender	Visit	Current PRN Dose	Date if PDAI (ddMMMMyyyy)	Total Mucosa (/120) – Activity	Anatomical Location	Erosion/blister	Number Lesion if <=3
400 mg QD	xxxxxxx	xx/F	xxx	400 mg QD	xxxx	xx	EYES	xx	xx
							NOSE	xx	xx
							BUCCAL MUCOSA	xx	xx
	...etc..								

F=Female; M=Male

Program: <program name (date, time)>, Path: <path>

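### Part B: a recalled CDA date entered after Week 5 can override an examined Week 5 non-response on the primary endpoint

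*SAP*

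**What the plan says.** All references are to the Part B SAP unless stated.

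- **Dating rule.** Section 3.4.7: "Date of CDA should be the first date CDA occurred i.e. a visit date or earlier date reported by the patient". Complete remission (CR), end of consolidation phase and relapse are dated in the same way.
- **Primary endpoint.** Section 5.4.1: "This is operationalized as meaning the first CDA is achieved on or before the Week 5 visit but after first dose of PRN1008". Responder status stands "even if the CDA status was not maintained or higher doses of prednis(ol)one were used after the first CDA". A patient whose Week 5 status is unknown is a non-responder. The same section says that CDA is assessed at the visits in the schedule.
- **What is collected.** The shell for Listing B.16.2.6.1 has, for each visit, a yes/no CDA status and a date if the answer is yes.
- **Who is analysed.** Section 5.4 uses the mITT population for efficacy. Section 3.2.4 requires a Week 5 disease assessment for entry to that population.
- **Steroid condition.** Section 4.2 rules out prednis(ol)one above 0.5 mg/kg at any time up to and including the Week 5 visit. Section 5.4.1 looks at one day only: "without prednis(ol)one >0.5 mg/kg on the date prior to the CDA will be considered as responders". The footnote to the primary table shell, B.14.2.1.1.1, tests the day before the assessment.

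**The concern.** Each visit yields two pieces of information about CDA: the investigator's finding that day, and a date that may come from the patient's memory. The plan does not say which prevails when they disagree. If the program takes the earliest entered CDA date, a date supplied at Week 9 can settle the Week 5 endpoint against the Week 5 examination.

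The unknown-status rule does not help, because an examined No is a known status. The clause accepting control that is later lost makes matters worse: a recalled Day 27 followed by a No on Day 29 looks like control gained and lost, which Section 5.4.1 counts as a response.

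For CDA, the rule can only move the date earlier than the visit. In an open-label, single-arm study, that direction favours the drug on the primary endpoint. It can also affect dose attribution, since the primary table assigns a responder to the dose taken before CDA. Suppose the patient was escalated at Week 5 for inadequate response and later recalls control from Day 27. The response would then be credited to the dose that had been judged inadequate.

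**Working it through.** **1. The plan's own precision figure.** Part B SAP 2.3 and Protocol 11.4 give 25 patients per part, a 50% response rate and an 80% interval of ±13%. The normal approximation reproduces this: 1.2816 × √(0.5 × 0.5 / 25) = 1.2816 × 0.1 = 0.128, or ±13%. The exact method planned in Section 5.4 is a little wider, about ±14.4 points at 12 or 13 responders out of 25.

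**2. Three hypothetical patients under the written rules.** Scheduled assessments fall on Days 15, 29 (Week 5) and 57 (Week 9). Background steroid is taken as 0.3 mg/kg and rescue as 1.0 mg/kg.

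- Patient 1: No at Week 5, Yes at Day 57, control recalled from Day 27, no rescue.
- Patient 2: rescue from Day 18, CDA seen at Day 29, control recalled from Day 16.
- Patient 3: No at Week 5, rescue from Day 43, CDA seen at Day 57, control recalled from Day 27.

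| Patient | 5.4.1 steroid test, visit date | 5.4.1 test, recalled date | 4.2 test, recalled date | Shell footnote test, recalled date |
|---|---|---|---|---|
| 1 | Non-responder | Responder | Responder | Responder |
| 2 | Non-responder | Responder | Non-responder | Non-responder |
| 3 | Non-responder | Responder | Responder | Non-responder |

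Patient 1 carries the point. Steroid plays no part, so all three steroid wordings give a response, and only the dating rule separates response from non-response. The recalled date lies 57 − 27 = 30 days before the visit at which it was entered and crosses the Day 29 examination.

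Patient 2 does not cross a recorded No if Day 15 was the last one. The outcome there depends on which steroid wording governs. For rescue given by Week 5, only Section 5.4.1 lets the recalled date step behind it.

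**3. Size.** One patient in 25 is 1/25 = 4 percentage points. The documents do not give the number of recalled dates, so the following is an assumed range, starting from 12 of 25 on examined status:

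| Patients reclassified | Rate | Exact 80% CI |
|---|---|---|
| 0 | 12/25 = 48% | 33.8% to 62.5% |
| 1 | 13/25 = 52% | 37.5% to 66.2% |
| 2 | 14/25 = 56% | 41.3% to 69.9% |
| 3 | 15/25 = 60% | 45.2% to 73.5% |

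Three such patients shift the estimate by 12 points, nearly the whole stated half-width. A smaller mITT population makes each step larger.

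**The case against.** The strongest reply is that the Week 5 case rests on silence. Section 3.4.7 asks for the date on which control first occurred, and a Day 27 date contradicts the same investigator's Day 29 finding. Protocol Section 13 promises validation checks, with discrepancies returned to the investigator. This is fair as far as it goes, but Section 13 is general: it names no CDA check and does not say whether the date or the status would be corrected. The gap remains.

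A second reply is that control normally begins between visits, so dating everything at the visit would itself delay event times. That stands for the time-to-event analyses, and the fix below allows for it.

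Several stronger readings are tempting but not supported:

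- **That recall lets rescued patients through.** Section 4.2 blocks rescue above 0.5 mg/kg given by Week 5, and the shell footnote blocks it when it is still in use on the day before the assessment. The rescue case shows a conflict of wording; it does not prove the point by itself.
- **That Part A and Part B times are not comparable for this reason.** Part A uses "Time to first CDA = Date of first CDA confirmed - Date of first dose + 1" but never defines when an event is confirmed, and its Listing 16.2.4.1.5 also has an achieved date beside the visit name.
- **That Section 4.7 should have listed the difference.** That section records changes from the protocol, not from the Part A SAP.
- **That back-dating is limited to the 14- or 28-day gap between visits.** No such limit is written, and Patient 1 exceeds 28 days.
- **That recalled dates always favour the drug.** Relapse is dated in the same way, and an earlier relapse counts against it. Relapse does not enter the primary endpoint.

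**Conclusion.** The point holds in a narrow form. As written, Sections 3.4.7 and 5.4.1 together allow a date recalled after Week 5 to turn an examined Week 5 No into a primary response, and no other text in the documents prevents it. A reader might infer that this will happen often, or that the reported rate is inflated; the documents support neither inference.

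The size is 4 percentage points per affected patient at 25 patients, with the number affected unknown. The conclusion assumes that the program takes the entered CDA date as the event date, which is the plain reading of Section 5.4.1. It is a cheap improvement worth making, because every mITT patient already has an examined Week 5 assessment and recall is not needed to fill a gap.

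**What to change.** 1. For the primary endpoint and the cumulative CDA and CR tables, count a response only if the status was recorded as Yes at a scheduled or unscheduled visit on or before the visit in question (Week 5 for the primary).
2. State that a recalled date may not precede a visit recorded as No.
3. In the time-to-event analyses, recalled dates between the last No and the first Yes visit may stay. Add a sensitivity analysis that uses visit dates.
4. Separately, reconcile the steroid condition in Section 4.2, Section 5.4.1 and the footnote to Table B.14.2.1.1.1, and state which governs. Items 1 and 2 do not settle Patient 2; this item does.

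The cost is SAP wording and a programming rule; visit status is already collected. The downside is that the response rate may fall slightly.

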3.5 Data Handling

3.5.1 Partial dates

Imputation of day, month and/or year for partial or missing AE onset dates will be performed as described below.

- Day, month and year missing
 - Leave as missing, no imputation. In this case, the adverse event will be considered as treatment emergent.
- Day and month missing
 - If year of start date is the same as the year of the 1st dose of PRN1008, then impute day and month as the day and month of 1st dose of PRN1008, ELSE
 - Impute day and month as 31-DEC, if the year is before the year of the 1st dose of PRN1008, ELSE

- Impute day and month as 01-JAN, if the year is after the year of the 1st dose of PRN1008
- Only day missing
 - If the year is the same as the year of the 1st dose of PRN1008
 - If the month is before the month of the 1st dose of PRN1008, then the last day of the month will be assigned to the missing day.
 - If the month is the same as the month of the 1st dose of PRN1008, then the day of the 1st dose of PRN1008 will be assigned to the missing day.
 - If the month is after the month of the 1st dose of PRN1008, then “01” will be assigned to the missing day.
 - If the year is before the year of the first dose of study drug, then the last day of the month will be assigned to the missing day.
 - If the year is after the year of the first dose of study drug, then “01” will be assigned to the missing day.

Imputation of day, month and/or year for partial or missing medication stop dates will be performed as described below if the medication is not flagged as “Ongoing”.

- Day, month and year missing
 - Leave as missing, no imputation. In this case, the medication will be considered as concomitant.
- Day and month missing
 - If year of stop date is the same as the year of the 1st dose of PRN1008, then impute day and month as the day and month of 1st dose of PRN1008, ELSE
 - Impute day and month as 31-DEC.
- Only day missing
 - If month and year of start date are prior to the month and year of the 1st dose of PRN1008, then impute day as 01, ELSE
 - Impute day as day of 1st dose of PRN1008.

Imputation of day and month for partial Date of PV Diagnosis (years) will be performed as described below.

- If only day is missing, impute as 01
- If day and month are missing, impute as 01-JAN

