15.4. Missing date imputation

15.4.1. Missing medication and AE stop dates imputation

For the purpose of inclusion in prior and/or concomitant medication tables, incomplete medication stop dates will be imputed as follows:

- If only day is missing, then set to the last day of the month.
- If only month is missing, then set to December.
- If both month and day are missing, then set to December 31.
- Completely or Year missing date will not be imputed.

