5.4.2.3 Cumulative Corticosteroid (CS) Usage

Cumulative corticosteroid (CS) usage per patient (mg) will be presented by treatment period (up to first 12 weeks, after first 12 weeks, entire treatment period and follow-up period), by dose level and overall in a table. To calculate this endpoint, the following steps will be followed:

Step 1: Select CSs with route = “ORAL” or “INTRAVENOUS”. The CSs will be converted into prednisolone/prednisone dosage equivalent using the below conversion chart.

CS medication	Conversion factor
Prednisone, Prednisolone	1
Hydrocortisone	0.25
Methylprednisolone, Methylprednisolone Sodium Succinate	1.25

Dexamethasone, Betamethasone	6.67
------------------------------	------

Step 2: The CSs usage will be converted to standard frequency using the following conversion chart.

Frequency	Unit	Conversion factor
QD, Q24H, ONCE, CONTINUOUS, BD PRN, PRN	mg	1
5 TIME A DAY	mg	5
QID	mg	4
TID	mg	3
2-3 DAILY	mg	2.5
BID	mg	2
QOD, EVERY 2 DAYS	mg	1/2
BIS	mg	2/7
QS, EVERY WEEK	mg	1/7
Any value	mg/day	1

Once the prednisolone/prednisone dosage equivalent and frequency are converted as above, each record of CSs taken will be converted to prednisolone with standard frequency (mg/day).

Step 3: The duration for each record of CS taken will be calculated using the formula: Duration = CS end date – CS start date + 1, in days. Any partial start or end date of CSs taken will be imputed using the algorithm specified in Section 3.5.1. If the CS start date is completely missing, then the date will be imputed as Week 1 Day 1, i.e. it is assumed that the medication is taken at the study entry. If the CS stop date is completely missing, then the date will be imputed as Date of End of Study, i.e. it is assumed that the medication is taken up to the end of study.

If the CS start date is before the Week 1 Day, then the CS start date will be replaced by the Week 1 Day 1; if the CS start date is after the date of Week 29 (Day 197) - 1, this record will not be used to summarize cumulative dose for CSs.

If the CS end date is after the date of Week 29 (Day 197) - 1, then the CS end date will be replaced by the date of Week 29 (Day 197) - 1; if the CS end date is before the study treatment start date, this record will not be used to summarize cumulative dose for CSs.

Note that above date adjustments only apply to cumulative CS dose calculation. Other analyses, where CS dose is needed, will use CS start and end dates as reported.

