Step 4: The “record” level cumulative CSs usage will be calculated as: record level cumulative dose = prednisolone/prednisone dosage equivalent * conversion factor for frequency * duration (days).

Step 5: The patient level cumulative CSs usage will be calculated as the summation of all the non-missing record level cumulative doses. If a patient had no CS records that meet the above criteria, the CS

cumulative dose is set as 0. The average daily CS usage in mg/day will be calculated as the cumulative doses divided by the number of days within a study period.

All CS usage will be presented in a listing showing record level prednisone dosage equivalent (mg), dose, frequency, route, start and stop dates. The total prednisone dosage equivalent in mg/kg will also be calculated by using the last measured weight prior to the current visit.

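### Part B's partial stop-date rule can make a steroid record count as zero or negative, and the shell cuts the 12- and 24-week steroid totals at last study drug for early stoppers

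*SAP*

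**What the plan says.** **Stop dates.** Part B SAP 3.5.1 covers medication stop dates that are partial and not flagged as ongoing. With day and month missing, the rule is "If year of stop date is the same as the year of the 1st dose of PRN1008, then impute day and month" as those of the first dose; in any other year the date becomes 31 December. With only the day missing, the rule asks "If month and year of start date are prior to the month and year of the 1st dose of PRN1008" and, if so, uses day 01. Otherwise: "Impute day as day of 1st dose of PRN1008".

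**Use for steroids.** Section 5.4.2.3, Step 3: "Any partial start or end date of CSs taken will be imputed using the algorithm specified in Section 3.5.1". Duration is end minus start plus one. The exclusion based on the end date is: "if the CS end date is before the study treatment start date, this record will not be used to summarize cumulative dose for CSs". Step 5: "The patient level cumulative CSs usage will be calculated as the summation of all the non-missing record level cumulative doses". A completely missing stop date is instead set to the end of study.

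**Part A.** Part A SAP 15.4.1 uses the last day of the month when only the day is missing. For a year-only date: "If both month and day are missing, then set to December 31".

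**Endpoint and shell.** Protocol 11.2 defines cumulative steroid use over the first 12 weeks, and also over 24 weeks in Part B. Endpoint 21 in Part B SAP 4.3 is use over 24 weeks. The footnotes to shell Table B.14.2.2.22.1 end the 12-week period at last study drug for patients who discontinue before Week 13. They end Period 2 and the entire 24-week period there for those who discontinue before Week 24. Later steroid belongs to the Follow Up row. On averages, 5.4.2.3 says: "The average daily CS usage in mg/day will be calculated as the cumulative doses divided by the number of days within a study period".

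**The concern.** The stop-date rule moves a partly known stop date to Day 1, although the steroid may have started weeks later. Nothing checks that the imputed stop falls on or after the record's own start, and nothing prevents a negative record from reducing the patient's total. The result is also out of order: a stop date with nothing known extends to the end of study, while one with a known year shrinks to Day 1.

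The shell raises a different problem. The endpoint is defined over calendar windows, but the table measures early stoppers only while they are on PRN1008. Some rescue branches in Protocol Appendix 1B start conventional immunosuppression and stop PRN1008 together, so the cut may be related to outcome. The results are meant to help design confirmatory trials (Protocol 11.4).

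**Working it through.** The plan gives no figure for this endpoint to reproduce. All doses, weights and dates below are illustrative assumptions.

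**1. Year-only stop date, same year as first dose (3.5.1, then 5.4.2.3 Steps 3 to 5)**

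The imputed end is Day 1. For a start on Day k, duration = 1 - k + 1 = 2 - k.

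| Start | Days counted |
|---|---|
| Day 1 (or earlier, moved to Day 1) | 1 |
| Day 2 | 0 |
| Day 29 | -27 |

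The end equals the treatment start and is not before it, so Step 3 does not drop the record.

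- 20 mg/day in use on Day 1 and stopped on Day 100: true 100 x 20 = 2,000 mg; counted 1 x 20 = 20 mg.
- 70 mg/day (1.0 mg/kg at 70 kg) from Day 29 to Day 84: true 56 x 70 = 3,920 mg; counted -27 x 70 = -1,890 mg.

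**2. Only the day missing, first dose on 20 March**

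- Start 25 June, stop some time in June: imputed 20 June; 20 - 25 + 1 = -4 days.
- Start in January, stop some time in March: imputed 1 March, before Day 1, so the record is dropped. Up to 12 days (20 to 31 March) are lost, or 240 mg at 20 mg/day.
- If the first dose falls on the 31st and the stop is in June, the imputed date is 31 June, which does not exist.

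The test on the start date may be a slip for the stop date. On that reading the January-to-March record ends on 20 March and keeps one day. The -4 day record is unchanged, because a June stop still falls in the second branch.

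**3. Shell windows**

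*PRN1008 stopped on Day 35, patient stays in follow-up:*

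- The 12-week row covers 35 of 84 days.
- Period 2 would run from the Week 13 visit (Day 85) to Day 35: 35 - 85 + 1 = -49 days, so its daily average is undefined.
- Follow Up runs from Day 36 to Day 197: 197 - 36 + 1 = 162 days, against 197 - 170 + 1 = 28 for a completer.

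With 10 mg/day to Day 35 and 70 mg/day afterwards, the 12-week row shows 10 x 35 = 350 mg (10 mg/day). Steroid recorded in the calendar window depends on how long the patient is followed:

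| Last day observed | Recorded by Day 84 |
|---|---|
| Day 35 | 350 mg |
| Day 60 | 350 + 70 x 25 = 2,100 mg |
| Day 84 | 350 + 70 x 49 = 3,780 mg (3,780 / 84 = 45 mg/day) |

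*PRN1008 stopped on Day 100:* the 12-week row is complete. Only the 24-week row is cut, at 100 of 168 days.

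**4. Labels**

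The footnotes refer to a Week 24 visit. The Part B schedule (SAP Table 1) goes from Week 21 (Day 141) to Week 25 (Day 169). The Follow Up row is marked [2], but footnote [4] defines it.

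**The case against.** **Rarity and visibility.** A negative year-only record needs a steroid started on study, not flagged as ongoing, with day and month of stopping unknown. Concomitant medication is reviewed at every Part B visit, and the data undergo validation checks and source verification (Protocol 13). Steroid records are listed with doses and dates, so a negative would be visible. This stands as a limit on likely frequency. It does not repair the rule, and a record cut from 2,000 mg to 20 mg would not look impossible.

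**Definition.** Section 5.4.2.3 presents use by treatment period, with follow-up separate. On-drug and off-drug rows fit that wording and are useful in their own right. That stands, so those rows need not be removed. They still do not deliver the protocol's endpoint. Part B SAP 4.7 lists no such change and says that reworded secondary endpoints keep their protocol meaning.

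**Assumed follow-up.** The gap between 350 and 3,780 mg needs a patient who stays in the study on a high steroid dose. If such patients leave when they stop PRN1008, there is little later steroid to count. That stands. The Completer table, limited to patients treated up to Week 25 (SAP 3.2.5), should be little affected.

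**Stronger readings.** A reader might infer any of the following:

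- *Early stoppers have no 12- or 24-week total, or their later steroid is lost.* A stop after Week 13 leaves the 12-week total whole, and later steroid is reported under Follow Up.
- *The primary endpoint is affected.* Nothing here shows that. Step 3 confines its date adjustments to cumulative dose and says other analyses use dates as reported.
- *The Part A restriction to patients reaching Week 13, or the choice of Part B analysis sets, is part of the same error.* These are stated population choices, and no error follows from them here.

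**Conclusion.** Both parts hold within limits. The stop-date defect follows from the text alone: a year-only stop in the first-dose year gives 2 - k days, which is zero from a Day 2 start, negative from any later start, and subtracted from the total. The day-missing branch can also place the stop before the record's start or on a date that does not exist.

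The shell departs from the protocol endpoint for patients who stop PRN1008 early. Those stopping before Week 13 lack both full totals and have a Period 2 that ends before it begins. Those stopping later, but before the end of the 24-week window, lack only the 24-week total.

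The milligram figures rest on assumed doses and follow-up. The numbers of partial dates and early stoppers are not given, so the size and direction of any bias are unknown; the documents do not support saying that the totals favour PRN1008. This is one descriptive secondary endpoint with no hypothesis test. It should be corrected, but it does not undermine the study.

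**What to change.** **Stop dates.** For Part B steroid records, adopt Part A's rule (last day of the month, or 31 December). Cap it at the end of the analysis window or study exit, and never place the stop before the record's own start. List every imputed record. Add a sensitivity analysis using the earliest possible stop date, because late imputation can overcount: 20 mg/day truly stopped on Day 5 is 100 mg, but could count as up to 84 x 20 = 1,680 mg at 12 weeks or 168 x 20 = 3,360 mg at 24 weeks.

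**Shell.** Add 12- and 24-week calendar-window rows, from Day 1 to the day before the Week 13 and Week 25 visits (Day 84 and Day 168 if the visit was missed), whether or not PRN1008 was stopped. Report days observed, and flag totals as incomplete for patients who left the study. Keep the existing rows if they are labelled on-drug and off-drug, with Period 2 shown as not applicable for stops before Week 13. Correct the Week 24 visit label and the Follow Up footnote mark.

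**Cost.** SAP and shell wording, and re-derivation from steroid records already collected. Steroid use after study exit stays unknown.
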